2 STUDY DESIGN

2.1 Synopsis of Study Design

BHV3000-301 is a Phase III, multicenter, randomized, double-blind, 2-arm placebo-controlled parallel-group study designed to assess safety and efficacy in the treatment of moderate to severe migraine.

After providing informed consent, subjects will first participate in the screening phase (3-28 day period) to determine eligibility for the study.

[figure not shown]
After randomization, the subject will be dispensed a single dose of the double-blind study medication to take home for up to 45 days. This study medication is to be taken when a migraine attack reaches moderate or severe intensity on the numeric rating scale (NRS) as indicated in the electronic diary (eDiary). The subject will complete an eDiary for up to 48 hours after taking the study medication. Subjects will record efficacy data in their eDiary and will telephone the study center immediately if a severe or serious adverse event occurs.

Subjects will return to the study site within 7 days of study treatment for review of the eDiary, assessment of medication compliance, and monitoring of tolerability and safety. If a subject has NOT experienced a migraine headache of sufficient severity within the 45 days after randomization, he or she will be withdrawn from the trial.

2.2 Randomization Methodology

The study will randomize approximately 1,200 subjects. The subjects will be randomized in a 1:1 ratio to receive rimegepant in a 75 mg tablet or matching placebo (see Figure 1). The randomization will be stratified by the use of prophylactic migraine medications (yes or no).

Figure 1: Study Schematic

2.3 Study Estimands

The tables that follow lay out the estimands corresponding to the study objectives. In these tables, the following abbreviations are used to describe the handling of intercurrent events for efficacy estimands:

NC=F: Non-Completers = Failure.

A subject with any missing data for an endpoint is classified as a treatment failure.

NC1=F: Non-Completers with more than 1 missing data point = Failure.

Subjects with more than 1 missing data point, other than at the 2, 24 or 48 hour data points, are classified as treatment failures. This applies to endpoints that are based on data from multiple time points. For example, for the durability endpoint of sustained pain freedom from 2 to 24 hours, the subjects should provide data at 2, 3, 4, 6, 8, and 24 hours. For NC1=F imputation, the data at 2 and 24 hour time points must be present or the subject is classified as a failure. However, any single data point may be missing at 3, 4, 6 or 8 hours without penalty. For sustained pain freedom from 2 to 48 hours, the data at 2, 24, and 48 hours are required to be present.

RM=F: Rescue Medication = Failure.

Subjects that take rescue medication before, or at, the time of the event of interest are classified as failures. If the time of rescue medication is missing, all events on or after the date of rescue medication are classified as failures.

2.3.1 Primary Estimands

The estimands corresponding to the co-primary endpoints for this study are shown in Table 1.

The population summary for all primary estimands is the difference in the percentage of subjects with a positive result ('risk difference') between the BHV-3000 and the Placebo treatment groups. This summary is computed using the modified Intent-to-Treat (mITT) population as defined in Section 4.1.

Objective	Pain Freedom at 2 hours post-dose	
Population	mITT	
Variable	Percent of subjects reporting no pain at 2 hours post-dose	
Intercurrent Events	NC=F; RM=F;	
Objective	Freedom from Most Bothersome Symptom (MBS)	
Population	mITT	
Variable	Percent of subjects reporting absence of their MBS at 2 hours post dose	
Intercurrent Events	NC=F; RM=F; Failure to report MBS = F; Study medication taken before reporting MBS=F.	

Table 1:Estimands for the Co-Primary Objectives

2.3.2 Secondary Estimands

The estimands corresponding to the secondary objectives are shown in Table 2.

The population summary for all secondary estimands is the difference in the percentage of subjects with a positive result ('risk difference') between the BHV-3000 and the Placebo treatment groups.

Photophobia Freedom at 2 hours post-dose	
mITT subjects with photophobia reported as present at migraine onset	
Percent of subjects reporting no photophobia at 2 hours post-dose	
NC=F; RM=F	
Phonophobia Freedom at 2 hours post-dose	
mITT subjects with phonophobia reported as present at migraine onset	
Percent of subjects reporting no phonophobia at 2 hours post-dose	
NC=F; RM=F	
Pain Relief at 2 hours post-dose	
mITT	
Percent of subjects who report mild or no pain at 2 hours post-dose	
NC=F; RM=F	
Nausea Freedom at 2 hours post-dose	
mITT subjects with nausea reported as present at migraine onset	
Percent of subjects reporting no nausea at 2 hours post-dose	
NC=F; RM=F	
Probability of Rescue Medication	
mITT	
Percent of subjects taking rescue medication	
None	
Functional Disability at 2 hours	
mITT	
Percent of subjects with a response of "normal" at 2 hours post-dose	
NC=F; RM=F	
Sustained Pain Freedom (2 to 24 hours; or 2 to 48 hours)	
mITT	
Percent of subjects pain free during the period of interest	
NC1=F; RM=F	
Sustained Pain Relief (2 to 24 hours; or 2 to 48 hours)	
mITT	
Percent of subjects who report no pain, or mild pain, during the period of interest	
NC1=F; RM=F	
Pain Relapse (2 to 48 hours)	
- · · · · · · · · · · · · · · · · · · ·	
mi i i subjects who report bain freedom at 2 nours post-dose	
mITT subjects who report pain freedom at 2 hours post-dose Percent of subjects who report any pain during the period of interest	

Table 2: Estimands for the Secondary Objectives

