5.7 Efficacy Evaluation

Unless otherwise noted, all efficacy analyses will be conducted using the mITT population as outlined below. All efficacy data will be included in listings by subject, study medication, and time point (as applicable). For efficacy analyses, baseline is considered as the assessment at the onset of the treated migraine. Subjects who were randomized twice will not be included in the efficacy evaluation.

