5.7.2 MBS Recored After IP is Taken

Subjects that record their MBS after taking the investigation product (IP) are considered failures for the analysis of MBS.

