5.7.4.1 Freedom from Photophobia, Phonophobia or Nausea at 2 Hours

Freedom from photophobia, phonophobia, and nausea are assessed, by treatment group, by tabulating the number of mITT subjects who reported the presence of the symptom at migraine onset who then report the absence of the symptom at 2 hours post-dose. Subjects who report the symptom at baseline, but have missing data at 2 hours post-dose will be imputed as failures (NC=F). Also, subjects in the analysis set that take rescue medications on or before providing their 2 hours post-dose data are imputed as failures.

The principal measurement for the associated symptoms (phonophobia, photophobia, and nausea) is made on a binary scale (0 = absent; 1 = present). An exploratory measurement of these symptoms was also made on a 4 point Likert scale (0=none, 1=mild, 2=moderate, 3=severe).

For these three endpoints, the difference between treatment groups, is evaluated by computing the common risk difference, using CMH weights (sample size weights), stratified by the use of prophylactic migraine medication (yes or no). The risk difference is tested at a two-sided alpha level of 0.05. If a stratum (prophylactic medication use: yes or no) has sparse data (less than 5 subjects) then the strata are pooled.

The results presented for the analysis of each symptom include those described in items (a) through (e) for the primary analysis of pain freedom (Section 5.7.3.1). In this case, the "risk" is the probability of being free from the symptom of interest at 2 hours post-dose. In addition, the following display will be created for each of the 3 symptoms:

• A table showing descriptive statistics for the 4-point scale, which includes the number and percentage of subjects reporting each of the 4 symptom levels at 2 hours post-dose, and the percentage of subjects with missing data, for each treatment group. The table will include exact (Clopper-Pearson) 95% CIs for each percentage.

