6.1 Extent of Exposure

Extent of exposure is measured by subjects providing self-repored drug exposure information in their eDiaries. As a check on this exposure data, drug accountability data are provided by the study center on the "Drug Accountability" CRF page.

The self-reported exposure data will be tabulated by treatment group, and will include:

- The number (and percentage) of randomized subjects that took study medication
 - The number and percentage who took the medication prior to providing baseline study migraine migraine characteristics
 - The number and percentage that took study medication after providing baseline study migraine characteristics
- The number and percentage of randomized subjects who reported not taking study medication
- The number and percentage of randomized subjects for whom no expossure data was reported

The drug accountability will be tabulated by treatment and overall, and will include:

- The number and percentage of randomized subjects to whom kits were dispensed
- The number and percentage of kits returned
 - The number and percentage of kits returned from which the IP was used
 - The number and percentage of kits returned from which the IP was not used
- The number and percentage of kits not returned

A cross tabulation of exposure and accountability data will be prepared. This will be done overall. For the exposure data the categories are: Took IP, Did not Take IP, and Unknown. For the accountability data, the categories will be: IP Used, IP not Used, and Unknown.

A listing will be prepared that indicates the exposure and accountability status of all randomized subjects. A patient identifier (PID) lisiting will be prepared if subjects had unknown exposure data, unknown accountability data, or for whom the exposure and accountability data did not match.

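### For photophobia, phonophobia and nausea freedom, the SAP does not require the onset symptom entry to precede the dose, so a foreseen late entry can set the denominator; the likely effect is small

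*SAP*

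**What the plan says.** The SAP foresees dosing before the onset entry. Section 6.1 will tabulate "The number and percentage who took the medication prior to providing baseline study migraine migraine characteristics".

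For MBS such subjects have a defined outcome. Table 1 in 2.3.1 lists "Study medication taken before reporting MBS=F", and 5.7.2 repeats it: "Subjects that record their MBS after taking the investigation product (IP) are considered failures for the analysis of MBS". The ad-hoc 3-hour MBS analysis in Appendix 3 carries the same rule.

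For the three symptom endpoints, Table 2 in 2.3.2 sets the population by the onset report ("mITT subjects with photophobia reported as present at migraine onset", "mITT subjects with phonophobia reported as present at migraine onset", "mITT subjects with nausea reported as present at migraine onset") and lists only NC=F and RM=F as intercurrent events. Section 5.7.4.1 likewise deals only with missing 2-hour data and rescue use.

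Section 5.7 says that "baseline is considered as the assessment at the onset of the treated migraine", with no condition on the time of dose. Table 6 ties the post-dose points to the time of dose, but gives the onset assessment an interval of Day 1 to 45, which a post-dose entry satisfies.

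Protocol 4.3.2 and the notes to its Table 1 tell patients to finish the onset questions before dosing. That governs conduct; it does not say how a breach is analysed.

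**The concern.** A symptom rating entered after the tablet is a post-treatment measurement. If it decides who is in the denominator, a late reporter whose symptom has already cleared is recorded as not having had it and leaves the analysis, while one whose symptom persists stays in. For those subjects the comparison no longer rests on randomization alone.

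MBS does not have this problem, because its denominator is the whole mITT population and late reporters remain in it as failures. The safeguard is thus missing from the endpoints where selection can occur. One subject can also be an MBS failure for reporting late and a photophobia success on the strength of the same late entry.

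The endpoints rank 1st, 2nd and 4th of 11 in SAP 5.2.5, and no sensitivity analysis is planned for them. The supportive symptom endpoints in Appendix 3 (1.5 to 1.7 and 4.1) use the same denominators.

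**Working it through.** **The plan's own figure.** SAP 5.1 states more than 95% power on each co-primary endpoint with 550 per arm. Pain freedom of 31.4% against 15.3% (protocol 1.3.2.8), two-sided 0.05 and pooled variance, gives more than 99.9% at 550 and also at 540 (90% of 600). The documents give no Phase 2b MBS rate. The symptom rates as proxies give more than 99.9% for photophobia and phonophobia and 99.98% for nausea. The joint bound is 1 - (0.05 + 0.05) = 90%. The statement is consistent.

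**Inputs for the selection effect.**
- True 2-hour rates p (protocol 1.4.2, rimegepant 75 mg against placebo): photophobia 41.9% and 24.1%; phonophobia 52.3% and 28.1%; nausea 67.4% and 51.2%.
- s, the share whose onset entry is post-dose: assumed 5% or 10%.
- f, the share of eventual 2-hour successes already symptom-free at the late entry: assumed 0.25 to 1.
- Symptom prevalence: assumed 60%, so 550 × 0.6 = 330 per arm.

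The documents give neither s, f nor prevalence.

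**Formula.** Among symptomatic subjects a fraction s·f·p, all eventual successes, drops out of numerator and denominator. Observed rate = p(1 - s·f)/(1 - s·f·p).

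**Photophobia, s = 5%, f = 0.5 on rimegepant and 0.25 on placebo.**
- Rimegepant: 0.419 × 0.975/(1 - 0.025 × 0.419) = 41.28%.
- Placebo: 0.241 × 0.9875/(1 - 0.0125 × 0.241) = 23.87%.
- Difference 17.41 points against a true 17.80, a shift of -0.39.

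**Shift in risk difference (percentage points).**

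| Assumption | Photophobia | Phonophobia | Nausea |
|---|---|---|---|
| s = 5%, f = 0.5 v 0.25 | -0.39 | -0.38 | -0.24 |
| s = 10%, f = 0.5 v 0.25 | -0.78 | -0.77 | -0.50 |
| s = 5%, f equal, 0.25 to 1 | -0.08 to -0.32 | -0.06 to -0.26 | +0.04 to +0.15 |
| s = 5%, f = 0.25 v 0.5 | +0.15 | +0.19 | +0.36 |
| s = 10%, f = 0.25 v 0.5 | +0.31 | +0.39 | +0.72 |

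At s = 20% with f = 0.5 v 0.25 the shifts are -1.62, -1.61 and -1.07. Power stays at or above 97% in every scenario run.

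**Subjects affected.** At s = 5% the late-reporting group is 550 × 0.05 = 27.5 per arm. Those who leave the photophobia denominator on rimegepant number 330 × 0.05 × 0.419 × (0.25 to 0.5) = 1.7 to 3.5.

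**No treatment effect.** With equal p and equal f the two observed rates are equal, so the shift is zero. With equal 2-hour rates of 30% but f = 0.5 v 0.25, the shift is -0.27 at s = 5% and -0.54 at s = 10%, again against rimegepant.

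**The case against.** The strongest reply is that the SAP nowhere says a post-dose entry counts as onset. A strict reading of onset, with the protocol instruction to answer before dosing, would exclude it, and 6.1 is only an exposure table. This stands in part: acceptance is inferred from silence. But no rule applies the strict reading, and 6.1 still calls the late entries baseline.

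The mITT definition narrows the route further. It requires moderate to severe baseline pain, so on the same reading a late reporter whose pain had already eased is outside mITT altogether. Only subjects whose symptom cleared while pain persisted can leave through a symptom denominator. This stands. It also shows that the missing pre-dose condition is not confined to the three symptoms.

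The different treatment of MBS can be defended, since nominating the MBS chooses which symptom is the subject's endpoint and protocol 6.3.2 requires that choice before dosing. That explains a rule for MBS; it does not justify having none for a denominator fixed by the same diary session.

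A reader might infer a bias in favour of rimegepant, or an inflated type I error at the first gate. The documents support neither. Subjects who leave are successes. If they are commoner on rimegepant, the loss works against it. If treatment changes neither symptoms nor reporting, selection is the same in both arms. Nor should the whole late-reporting group be counted as misclassified, since only those whose symptom had cleared change place.

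**Conclusion.** The point holds as a gap in definition. The SAP expects late onset entries, provides for them in MBS only, and leaves three gated secondary endpoints with denominators that a post-treatment rating can determine.

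Under the assumed 5-10% late reporting with earlier clearing on rimegepant, each risk difference shifts by less than 1 point, against rimegepant. A shift towards rimegepant needs other assumptions, such as earlier clearing on placebo, and also stays below 1 point at these shares. All of this rests on assumed values of s, f and prevalence. The eventual count in the 6.1 table would settle s.

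This is a cheap improvement in consistency. It is not a demonstrated threat to the primary result, to type I error or to the testing sequence.

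**What to change.** - **Denominators.** In Table 2 and 5.7.4.1, define each symptom denominator as mITT subjects whose eDiary entry recorded before the time of dose reports the symptom present. Whether such an entry exists is settled at the moment of dosing, so response cannot influence it. The timing flag is already needed for MBS and for 6.1. Carry the definition into the matching Appendix 3 endpoints.
- **Leave mITT and the MBS failure rule unchanged.** A general pre-dose baseline in 5.7 would leave subjects with no pre-dose entry without a baseline, remove them from mITT, and empty the MBS rule.
- **Sensitivity analysis.** Keep late reporters in each symptom denominator as failures. This should not be the main analysis. Even if only truly symptomatic late reporters are counted, the difference shrinks by the factor 1 - s (photophobia at 5%: 17.8 × 0.95 = 16.9, a loss of 0.9 points against 0.39 if nothing is done). It also counts people who may never have had the symptom.
- **Timing.** Settle this before unblinding. Appendix 3 is written in the past tense; if the data were already unblinded, report the revised analysis as supportive.
- **Separate correction.** Section 5.7.3.2 at one point makes subjects who reported their MBS before taking the product failures, the reverse of Table 1, 5.7.2 and its own later text. These must be reconciled.

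**Cost.** A clause in each of two places and one extra table. At s = 5% and 60% prevalence, about 330 × 0.05 = 16.5 symptomatic subjects per arm fall outside each symptom denominator. With about 313 left per arm, nausea power is still about 98.6%.

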2.3.3 Exploratory Estimands

The estimands corresponding to the exploratory objectives are shown in Table 3.

Objective	Functional Disability at 24 hours	
Population	mITT	
Variable	Percent of subjects with a response of "normal" at 24 hours post-dose	
Intercurrent Events	NC=F; RM=F	
Pop. Summary	Percentage within each treatment group (BHV3000 & Placebo)	
Objectives	Pain Relief at 30, 60 or 90 minutes post-dose	
Population	mITT	
Variable	Percent of subjects who report pain as mild or none at the time point of interest	
Intercurrent Events	NC=F; RM=F	
Pop. Summary	Percentage within each treatment group (BHV3000 & Placebo)	
Objectives	Preference of Medication	
Population	Treated subjects who: 1) answer "yes" to the lead-in question (i.e. "Have you ever taken migraine medication?") and provide preference of medication data	
Variable	Percentage of subjects who prefer study medication to previous migraine medications	
Intercurrent Events	Observed analysis. No accounting for intercurrent events.	
Pop. Summary	Percentage within each treatment group (BHV3000 & Placebo)	
Objectives	Pain Relief, on a 4 point scale, at all time points	
Population	mITT	
Variable	Percent of subjects who report pain as none, mild, moderate or severe	
Intercurrent Events	NC=F; RM=F	
Pop. Summary	Percentage of each response, in each treatment group (BHV3000 & Placebo)	
Objectives	Migraine Quality of Life Questionnaire	
Population	mITT	
Variable	Total score on the MQoLQ	
Intercurrent Events	Observed analysis. No accounting for intercurrent events.	
Pop. Summary	Average total score within each treatment group (BHV3000 & Placebo)	
Objective	Safety and Tolerability	
Population	All treated subjects	
Variables	Multiple	
Intercurrent Events	Subjects analyzed as treated. No accounting for intercurrent events	
Pop. Summary	Multiple (discussed under Section 6, "Safety Analyses")	
Objective	Sheehan Suicidality Tracking Scale	
Population	All treated subjects	
Variables	Change from baseline in the total score	
Intercurrent Events	Subjects analyzed as treated. No accounting for intercurrent events	
Pop. Summary	Percentage of subjects, by treatment group, in each of 5 categories ($<-1, -1$, no change, 1, >1)	

Table 3: Estimands for the Exploratory Efficacy Objectives

4 SUBJECT POPULATIONS

4.1 **Population Definitions**

The following subject populations will be evaluated and used for presentation and analysis of the data:

- Enrolled subjects: patients who sign an informed consent form and are assigned a subject identification number
- Randomized subjects: enrolled subjects who receive a randomization treatment assignment from the interactive web response system (IWRS), regardless of the treatment they actually received or subsequent withdrawal from treatment
- Treated subjects: enrolled subjects who take any amount of study therapy (rimegepant or placebo)
- Modified Intent-to-Treat (mITT) subjects: Randomized subjects who are randomized only once, take study medication, have a baseline migraine of moderate to severe intensity, and who provide at least one post-baseline efficacy data point. Subjects that re-enrolled in the study, and were randomized on two or more occasions are not included in the mITT population.

4.2 **Protocol Deviations**

A protocol deviation is any variance from the approved protocol, either intentional or unintentional. The possible categories for all protocol deviation are as follows:

- Informed Consent
- Inclusion/Exclusion Criteria (specify #)
- Concomitant Medication
- SAE Reporting
- Regulatory
- Drug Storage/Preparation
- Drug Administration
- Visit Schedule

- EPro Diary Noncomplinace
- Noncompliance (i.e., trends, missed assessments).

A significant protocol deviation is any deviation that could impact subject safety or the integrity of the trial. For the purposes of this study, significant protocol deviations will be defined as the following:

- Inadequate informed consent or initiation of study procedues prior to completing the informed consent
- Enrollment of subjects not meeting the inclusion/exclusion criteria
- Unreported SAEs
- Improper breaking of the blinding of the study
- Use of prohibited medication as defined by the protocol
- eDiary non-compliance with primary and secondary endpoints (2, 24, or 48-hour post-dose assessment
- Repeated deviations of the same nature for a given site or patient
- Initiation of rescue medication(s) prior to primary endpoint at 2-hours

The sponsor, or designee, will be responsible for producing the final protocol deviation file (formatted as a Microsoft Excel file). This file will include site, subject ID, deviation date, deviation type, and a description of the protocol deviation.

All protocol deviations (with the exception of those related to rescue medication and missed eDiary assessments) will be presented in a data listing. Handling of rescue medication and missed eDiary assessments are described in the statistical methods section of this SAP.

